2. * Which option(s) best describe the way(s) this study's procedures will be conducted? (Select all that apply.) This information may be used by the IRB in triaging studies during an emergency.

- In-person interactions / interventions with participants
- Remote interactions / interventions with participants
- Secondary data/specimen analyses with or without contact with study participants

3. * Would it be possible to convert in-person activities in your study to remote if there is an approved contingency protocol?

No, not possible to convert to remote activities

4. * Does this study involve greater than minimal risk:

- Yes No

5. * Review type requested: (subject to IRB approval):

- Full Board
- Expedited
- Exempt

6. * Is this study initiated by a VCU investigator or a sponsor:

- VCU Investigator initiated
- Sponsor or industry initiated

The IRB has determined that the selected types of anticipated individual and social benefit apply to this study

The below information is read-only to investigators, and the categories are set by the IRB during review. All categories will appear blank until the IRB has made a determination. If a category is not checked, it does not apply to this study. This information may be used by the IRB in triaging studies during an emergency situation.

Scientific benefit

Initial Setup Complete

Protocol Progress:

- **INITIAL SETUP**
- ② BACKGROUND, RATIONALE & GOALS
- ③ RESEARCH PLAN
- ④ CONSENT PLAN
- ⑤ RISKS, PRIVACY & CONFIDENTIALITY
- ⑥ POPULATIONS WITH SPECIAL CONSIDERATIONS
- ⑦ INSTITUTIONAL REQUIREMENTS
- ⑧ DOCUMENTS

Click Continue below to go to the next section

Background, Rationale and Goals

1. * Describe the study's background and what is currently known from the scientific literature, including citations, or upload a citation list in document upload. Use lay language whenever possible.

The aim of this proposal is to determine if utilizing an affordable tool like microstimulation utilizing a TENs unit and applying the stimulation to the ear through an ear clip does improve vagal modulation. This can be easily done at home by utilizing the microstimulation for 2 hours a day and measuring vagal modulation before and after. Previous research investigating this had participants use the unit for 2 hours as well. ([name] et al., 2019), however the data from this study was inconclusive, and therefore this study aims to demonstrate effectiveness of the unit usage on heart rate variability (HRV).

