The overarching hypothesis of this proposal is that auricular vagal micro-stimulation improves vagal modulation.

Based on prior experience, in more than half the subjects, we expect high-frequency heart rate variability (hfHRV) to improve by 10% from baseline to week 4.

3. * Describe the study's specific aims or goals. Use lay language whenever possible.

To determine if the auricular microstimulator produces the expected increase in HRV.

4. * Describe the scientific benefit or importance of the knowledge to be gained:

Potential conclusions would include that the vagal stimulator inhibits the neuroinflammatory cascade and that neuro-inflammation plays a major role in pediatric FGID, a currently open question.

5. * Describe any potential for direct benefits to participants in this study:

The TENS unit has the potential to decrease symptoms in participants with FGID. We cannot guarantee this will help, hence why we are doing the study.

6. * Describe any potential for direct social impact in this study . For example, any engagement with specific communities to respond to community-identified needs, or ways the study will strengthen the well-being of the specific communities if applicable:

If this auricular TENS unit device produces the expected results, it will:

- 1) provide a portable, affordable tool to decrease symptoms in FGID
- 2) corroborate that increasing vagal modulation improves symptoms in FGID

7. Upload a supporting citation list if applicable:

	Document Name	Document	Version	Date Modified	Uploaded By	Type	Approved
View	FGID Assent/Parental Permission	TENS FGID Assent V10.pdf	0.23	4/23/2024 11:25 AM	[name]	Consent/Assent/Information Sheet	Yes
View	Healthy Control Assent/Parental Permission	TENS HC Assent V10.pdf	0.23	4/23/2024 11:25 AM	[name]	Consent/Assent/Information Sheet	Yes
View	Healthy Control Consent	TENS HC Consent V10.pdf	0.22	4/23/2024 11:24 AM	[name]	Consent/Assent/Information Sheet	Yes
View	FGID Consent	TENS FGID Consent V10.pdf	0.22	4/23/2024 11:24 AM	[name]	Consent/Assent/Information Sheet	Yes
View	Best Practice Alert MyChart Message Script	Best Practice Alert MyChart Message Script V2.docx	0.03	3/13/2024 3:52 PM	[name]	Recruitment/Advertising	Yes
View	Flyer	TENS Flyer (Undesigned Language Only) V4.docx	0.07	3/13/2024 3:51 PM	[name]	Recruitment/Advertising	Yes

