View	[name] CV	[name] CV Signed.pdf	0.01	10/20/2022 11:43 AM	[name]	CV/Biosketch	Yes
View	Basic Participant Information	BasicInformation.pdf	0.01	10/18/2022 3:38 PM	[name]	Research Measure	Yes
View	Screening Form	ScreeningForm.pdf	0.01	10/18/2022 3:37 PM	[name]	Research Measure	Yes
View	[name] CV	[name] CV.docx	0.01	9/12/2022 4:52 PM	[name]	CV/Biosketch	Yes

Study Population

1. * Provide the maximum number of individuals that

1. May participate in any study interaction or intervention (Including screening, consenting, and study activities)

AND/OR

2. You obtain any data/specimens about (regardless of identifiability)

at VCU and at other sites under the VCU IRB's oversight. See the help text for additional guidance.

100

2. If this is a multi-Center Project, what is the maximum anticipated number of subjects across all sites?

Not multi-center

3. * Provide justification for the sample size by explaining how you arrived at the expected number of participants and why this number is adequate for answering the research questions:

Our power estimates show that 28 or more measurements/surveys are needed to have a confidence level of 95% that the actual change in HRV d/t TENS unit use is within $\pm 5\%$ of our measurements of HRV. We estimate about a 30% compliance rate, so we arrived at 100 to account for dropouts and screen fails. We are not aiming to recruit an equal number of FGIDs/non-FGID, because our main aim is to figure out if the TENS unit improves vagal modulation in general, not to compare the degree of variability between FGID and non-FGID subjects.

4. * List the study inclusion criteria:

Female

12 – 21 years old

Either diagnosed OR not diagnosed with chronic idiopathic nausea, functional abdominal pain, dyspepsia and/or irritable bowel syndrome.

English speaking

5. * List the study exclusion criteria:

Patients who are unable to stand upright during the heart rate variability recording

Patients with a known bleeding disorder

Patients with swollen, infected, inflamed, or other skin eruptions on outer ear

Patients with epilepsy

Patients with any implanted cardiac pacemaker or defibrillator

Patients with serious arterial circulatory problems in the lower limbs

Patients with abdominal or inguinal hernia

Patients who are pregnant

Any unstable medical condition, such as renal disease, uncontrolled diabetes, etc.

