If the subject experiences a medical emergency during the Week 0 or 4 in-person visits, the VCU Public Safety emergency response process will be activated. In a situation that calls for an advanced medical response, this process includes the following steps:

- a. VCU public safety working with a 911 dispatcher to direct emergency personnel to the building
- b. Emergency vehicle transporting to VCU emergency department

5. * Describe criteria for when the investigator would withdraw an individual participant from the study; such as safety or toxicity concerns, emotional distress, inability to comply with the protocol, etc.:

If the participant is not able to wear the TENS unit due to physical discomfort, severe irritation/scabbing, or they cannot commit to using the unit for 2 hours a day for the duration of the study, they will be withdrawn from the study.

Should the participant require new medication during the duration of the study that may affect gastrointestinal symptoms, vagal modulation or immune response, or their HRV measurement indicates an abnormality, the PI may withdraw the participant. The Epic build of this study will send the study team an alert for new medications for FGID participants. New medication usage will be assessed on a case-by-case basis by the PI and they will make a decision on whether to keep or withdraw the participant. All participants will also be asked to detail the start or plans to start a new medication.

6. * Summarize any pre-specified criteria that would trigger the investigator/sponsor/monitoring committee to stop or change the study protocol due to safety concerns:

The stopping points for the study include the request to stop by the patient as well as the inability to recruit participants or unexpected adverse events that might result in stopping the study.

Data and Safety Monitoring

Data and safety monitoring is a system for checking the study's data at regular intervals over the study period to identify and address issues that could affect the safety of research participants. This requirement is in accordance with 45 CFR 46.111.

The purpose of data and safety monitoring plan is to set forth study team procedures for monitoring/addressing:

- Participant safety (physical, psychological, etc.)
- Data validity
- Early stopping (termination) based upon changes in risks and benefits.

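### The stated precision of ±5% from 28 measurements is not supported: 28 probably comes from a survey formula that does not apply to an HRV change, and otherwise rests on an unstated SD of about 13% or less

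*Protocol*

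**What the plan says.** Protocol, Study Population, question 3: "Our power estimates show that 28 or more measurements/surveys are needed to have a confidence level of 95% that the actual change in HRV" is within ±5% of the measured value. The next sentence moves from 28 to 100: "We estimate about a 30% compliance rate, so we arrived at 100 to account for dropouts and screen fails". The same answer gives the target of inference: "our main aim is to figure out if the TENS unit improves vagal modulation in general".

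Study Population, question 1, shows that 100 is a maximum that already counts people who are only screened or consented. It is not a number enrolled or analysed.

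The expected effect is in Background, Rationale and Goals, question 2, and is repeated under Study Procedures, question 1: "in more than half the subjects, we expect high-frequency heart rate variability (hfHRV) to improve by 10% from baseline to week 4". The reason for the study is in question 1 of the same Background section: "the data from this study was inconclusive, and therefore this study aims to demonstrate effectiveness of the unit usage on heart rate variability".

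The protocol gives no SD of the change, power, significance level, test or formula. In the sample-size text it does not say which HRV measure or scale is meant.

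**The concern.** A half-width for a continuous change cannot be computed without an SD, and none is given. The text calls the result a power estimate but gives only a confidence level and a margin, which together describe precision.

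The figure matters because readers will set it beside the expected 10% improvement. ±5% around 10% suggests that 28 participants would separate the effect clearly from zero. If the true half-width is wider, a study started because earlier data were inconclusive could end the same way, although its protocol had said the number was enough.

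**Working it through.** **Inputs from the protocol:** 28; 95% confidence (z = 1.96); ±5%; 30% compliance; cap of 100. **Not in the protocol, assumed here:** p = 0.5 for a proportion; any SD; 80% power and a two-sided 5% paired t test. I read ±5% as ±5 percentage points on a percent-change scale.

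**1. Reproducing 28 from the protocol's own figures.** The survey formula for a proportion gives n0 = 1.96² × 0.25/0.05² = 384.15 (using unrounded z). With the finite-population correction, n = n0/(1 + (n0 − 1)/N):

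| Population N | n | Rounded up |
|---|---|---|
| 28 | 26.2 | 27 |
| 29 | 27.03 | 28 |
| 30 (= 0.30 × 100) | 27.9 | **28** |
| 31 | 28.8 | 29 |
| 100 | 79.5 | 80 |

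Of these populations, only 29 and 30 return 28, and 30 is the protocol's own yield.

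**2. What that formula would mean.** The margin for a proportion with 28 observed is 1.96 × √(0.25/28) = 0.185, or ±18.5 points. The correction factor √((30 − 28)/29) = 0.263 brings this to 0.049, so the ±5 comes almost entirely from having observed 28 of a supposed 30. That correction is valid only if the 30 are the whole population of interest, whereas the protocol wants the effect in general. Without it, ±5 points for a proportion needs 385. The route is also circular: 30 is 30% of 100, and 100 is what the 28 is used to justify.

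**3. The alternative: precision of a mean percent change in 28 pairs.** The half-width is t(0.975, 27)/√28 × SD = 0.388 × SD. For ±5 points the SD must be at most 5/0.388 = 12.9% (t), or 5 × √28/1.96 = 13.5% (z). For illustrative SDs, the half-width at n = 28 is 3.9 points at SD 10%, 5.8 at 15%, 7.8 at 20% and 11.6 at 30%.

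**4. From 28 to 100.** 28/0.30 = 93.3, rounded up to 94, which 100 covers; 0.30 × 100 = 30. This step is consistent.

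**5. What about 30 completers deliver.** The half-width for a mean change is t(0.975, 29)/√30 × SD = 0.37 × SD. Under the assumed paired t test at two-sided 5% and 80% power, the detectable mean change is 0.53 SD, so a 10% mean change needs an SD of at most 18.9%. That limit depends on the assumptions: across 28 to 30 analysed, 80% to 90% power, and t or normal calculation, it runs from 15.7% to 19.6%. Power with 30 completers would be 94% at SD 15%, 75% at 20% and 42% at 30%. These SDs show the range and are not estimates for this population.

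**The case against.** The strongest reply is that the survey formula is reverse-engineered. Neither p = 0.5 nor a finite-population correction is written down, and 28 also follows from an ordinary precision calculation with an SD of about 13%. The reference to surveys has an innocent explanation, since the study collects questionnaires and diaries. This stands: the match is probable, not proven. It does not rescue the ±5%, because the alternative needs an SD that the protocol never gives.

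A second reply is that a formula for a proportion suits a hypothesis about more than half the subjects. But the protocol attaches ±5% to the change in HRV, not to a share of responders. Even for a share, 28 gives ±18.5 points once the correction is removed.

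A third is that the Background section describes the work as preliminary, so a justification by precision is reasonable. I agree that precision is a fair basis; the stated precision still has to follow from stated inputs.

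Three stronger readings are tempting, and the documents do not support them:
- **That 100 is too few.** With no SD in the protocol, adequacy cannot be judged; at SD 15% the assumed test would have 94% power.
- **That the protocol plans for a 10% mean change among 100 enrolled.** It expects 10% in more than half the subjects, and 100 is a cap that includes people screened.
- **That the inflation to 100 is wrong.** It is consistent with the stated 30%.

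**Conclusion.** The point holds in this limited form. The protocol claims ±5% at 95% confidence for the HRV change from 28 measurements, and its figures do not support that on either plausible reading. On the more likely one, the formula does not apply to a continuous change, is circular, and gives a margin 3.7 times as wide (18.5/5) once the correction is removed. On the other, the claim is true only if the SD of the percent change is at most 12.9% (t) or 13.5% (z), which is not stated. Which calculation was used is an inference.

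The 18.9% limit for detecting a 10% mean change rests on a test, significance level and power that the protocol does not specify, and on reading its expectation as a mean. It describes what the design could deliver and does not show that the study is underpowered. The text should be corrected because it is the protocol's only statement of why the number is adequate.

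**What to change.** State which calculation gave 28.

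- **If an SD of about 13% or less can be supported:** keep 28, call it a precision estimate, and give the HRV measure, the scale, the SD and its source.
- **Otherwise:** withdraw the ±5% and the term power estimate, and replace them with text such as:

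> The unit of analysis is a participant with hfHRV at both visits. From a maximum of 100 people, including those screened, about 30 such participants are expected. The 95% confidence interval for the mean percent change will have a half-width of about 0.37 times the SD of the change. For orientation, assuming a paired t test at two-sided 5% and 80% power, the detectable mean change is 0.53 SD; a mean change of 10% would need an SD of at most about 18.9%. The expectation in the hypothesis concerns the share of participants who improve by 10%, not the mean change.

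The cost is one rewritten paragraph and a less favourable stated precision. No increase in enrolment and no interim look at the SD is needed.

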Requires new medication during the 4 weeks of the study that may affect the gastrointestinal symptoms, vagal modulation or immune response.

Practices over 1 hour of aerobic activity a day

Daily practice of abdominal breathing (yoga)

6. * Will individuals with limited English proficiency be included in or excluded from this research?

Included

Excluded - safety concerns if participants are unable to communicate with the study team

Excluded - instruments/measures only validated in English

Excluded - no prospect of direct benefit to individual participants

- Excluded - minimal risk study
- Excluded - lack of budget/resources for translation and interpretation [provide an explanation in next question]
- Excluded - other reason [provide an explanation in next question]

7. Justify the inclusion and exclusion criteria if you are either targeting, or excluding, a particular segment of the population / community. Provide a description of the group/organization/community and provide a rationale.

The sex restriction is because there is a disproportionate representation of females having functional disorders. Having male participants in the study may lower the study's external validity and findings may not be generalizable to females with a male population included.

The TENS unit uses an ear clip and we do not want to disrupt the healing process for ear problems.

We want to exclude people with the conditions listed above (bleeding disorders, epilepsy, circulatory problems, hernias, pregnancy, any other unstable condition) because it will skew the data by decreasing the ability to properly assess heart rate variability without confounding variables.

We do not know how the presence of cardiac pacemaker or defibrillators will alter our data nor do we have solid research on the safety of using TENS with these devices, so we are excluding this population.

We are excluding those who start a medication during the 4 weeks of the study that may affect the gastrointestinal symptoms, vagal modulation or immune response because we do not know how this will alter our data or interact with the TENS unit.

Participants who engage in over 1 hour of aerobic exercise or daily practice of yoga will be excluded because we will not be able to pinpoint whether HRV changes are due to the use of the TENS unit or the exercise/yoga.

Background, Rationale & Goals Section Complete

Protocol Progress:

● **INITIAL SETUP**

● **BACKGROUND, RATIONALE & GOALS**

③ RESEARCH PLAN

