④ CONSENT PLAN

⑤ RISKS, PRIVACY & CONFIDENTIALITY

⑥ POPULATIONS WITH SPECIAL CONSIDERATIONS

⑦ INSTITUTIONAL REQUIREMENTS

⑧ DOCUMENTS

Click Continue below to go to the next section

Study Procedures

1. * Describe the study hypothesis and/or research questions. Use lay language whenever possible.

The overarching hypothesis of this proposal is that auricular vagal micro-stimulation improves vagal modulation.

Based on prior experience, in more than half the subjects, we expect high-frequency heart rate variability (hfHRV) to improve by 10% from baseline to week 4.

2. * Describe the study's specific aims or goals. Use lay language whenever possible.

To determine if the auricular microstimulator produces the expected increase in HRV.

3. * Choose all types of recruitment materials that may be used and upload them below:

- E-mail invitations**
- Phone Solicitation scripts (i.e. cold calls or random-digit-dialing)
- Flyers, Mailed Letters or Newspaper/TV/Radio Ads**
- TelegRAM announcements**
- Website text
- Study-specific web sites (provide the design and text)
- Social Media**
- EPIC MyChart Patient Portal research study descriptions**
- Psychology Research Participant Pool (SONA) study descriptions
- Scripts for announcements made to groups
- Other recruitment document**
- No recruitment materials

4. * If Other was selected above, describe the recruitment document that will be used:

Scripts for individual participants

5. * Describe the study procedures/methods for identifying and recruiting participants. Address all of the following three aspects of recruitment in your response.

1. Identification of potentially eligible participants or secondary data/specimens of interest.

- What database(s) will be queried to identify secondary data/specimens
- How VCU Informatics or VCU IRDS will be used for cohort identification (when applicable, see help text)
- How potential participants' contact information will be obtained

2. Recruitment procedures to invite participation in the study (when applicable):

- How each of the written or verbal recruitment materials and reminders (selected above) will be used
- Who will contact, approach, or respond to potential participants
- Locations where recruitment procedures will take place
- The timing and frequency of recruitment attempts

3. Eligibility screening prior to consent and how those activities will be carried out (when applicable)

See the help text for additional guidance.

1.

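### The aim and the sample-size sentence attribute the HRV change to the device, but everyone uses the active unit, so the device's share of the four-week change is not identified

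*Protocol*

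**What the plan says.** Three places in the protocol use causal language.

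- **Specific aims** (Background, Rationale and Goals, Q3; repeated in Study Procedures, Q2): "To determine if the auricular microstimulator produces the expected increase in HRV".
- **Background, Rationale and Goals, Q1**: "this study aims to demonstrate effectiveness of the unit usage on heart rate variability (HRV".
- **Study Population, Q3** (sample size): 28 or more measurements are said to give 95% confidence, to within ±5%, about "the actual change in HRV d/t TENS unit use".

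The procedures (Study Procedures, Q7) describe one course for all participants. HRV is recorded at week 0, the unit is used for two hours daily over four weeks, and HRV is recorded again at week 4. Within each visit HRV is recorded before, during and after stimulation, always in that order. No sham, untreated arm or randomisation is described.

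The only quantified expectation is in the hypothesis (Background Q2; Study Procedures Q1): in more than half of the subjects, high-frequency HRV (hfHRV) should rise by 10% from baseline to week 4. The Background section also says that the study is for preliminary data.

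**The concern.** A before-and-after change in a single treated group is the device effect plus everything else that moves between the two visits. The second visit is familiar, participants know that they are using an active unit, and extreme baseline values tend to move back towards the average. With no concurrent group exposed to the same influences, the data cannot divide the total into its parts.

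The investigators accept that attribution matters. Study Population, Q7 excludes frequent exercisers and daily yoga practitioners because otherwise "we will not be able to pinpoint whether HRV changes are due to the use of the TENS unit or the exercise/yoga". Exclusions of that kind remove some named causes. They do not remove shifts common to all participants.

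At stake is what the trial may conclude. As written, a favourable result would be reported as effectiveness, with a ±5% margin that appears to apply to the device effect. No later analysis plan can recover the attribution, because the information is not collected.

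**Working it through.** **Step 1. What the design estimates.** For each participant, observed change = device effect + non-device change + random variation. The mean over participants estimates device effect + mean non-device change. Nothing in the design estimates the second term by itself. The FGID and non-FGID groups do not form a treated/untreated contrast: both use the unit, and Study Population, Q3 says that comparing them is not intended. The before/during/after recordings within a visit have no sham and a fixed order, so stimulation is mixed with time elapsed and time lying down.

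**Step 2. Can 28 be reproduced?** Inputs from Study Population, Q3: n = 28, 95% confidence, ±5%, 30% compliance, ceiling of 100. No SD is given. Two readings both lead to 28:

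- *Half-width for a mean change.* SD = 5 × √28 / t(0.975, 27) = 5 × 5.292 / 2.052 = 12.9 percentage points (13.5 with 1.96 in place of t). This SD is solved backwards from 28, so it confirms nothing.
- *Survey formula for a proportion.* n₀ = 1.96² × 0.25 / 0.05² = 384.1. With finite-population correction for N = 30 (30% of 100), n = 384.1 / (1 + 383.1/30) = 27.9, that is 28. Here p = 0.5 and N = 30 are assumptions.

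On the second reading ±5% says nothing about how variable HRV change is. An SD of 12.9 is therefore one assumption among several, and a range is needed.

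**Step 3. Illustration of what a common drift does.** Assumptions, none from the documents: no device effect, 28 completers, normally distributed percentage changes, and drift and SD as listed.

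*Rule A, the protocol's own expectation:* at least 15 of 28 improve by 10% or more. Each person's chance is p = P(Z > (10 − drift)/SD), and the trial's chance is P(Binomial(28, p) ≥ 15).

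*Rule B, not stated in the protocol:* a two-sided 5% t test of mean change against zero is significant in the positive direction. The chance comes from the noncentral t with 27 df and noncentrality drift × √28 / SD.

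| Assumed SD | p at 5% drift | Rule A, 5% drift | Rule B, 5% drift | Rule A, 10% drift |
|---|---|---|---|---|
| 12.9 | 0.349 | 3.3% | 51% | 42.5% |
| 20 | 0.401 | 10.5% | 25% | 42.5% |
| 30 | 0.434 | 18% | 13% | 42.5% |
| 50 | 0.460 | 27% | 7% | 42.5% |

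In the last column the SD drops out: with a 10% drift each person's chance of reaching 10% is one half, and P(Binomial(28, 0.5) ≥ 15) = 0.425.

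**The case against.** **The study is declared preliminary.** A single-group before-and-after design is ordinary at that stage, the form asks for lay language, and the exclusions for exercise, yoga and new medication limit some competing explanations. All of this stands as a defence of the design. It does not defend the claim: calling the data preliminary does not make an uncontrolled change attributable to the device, and the sample-size sentence is a technical statement about what the ±5% applies to.

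**The within-visit recordings add information.** They do, on short-term change around stimulation. Without a sham or a varied order they do not isolate the device, and they do not bear on drift over four weeks.

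**A stronger reading that the documents do not support.** A reader might infer that a 5% drift would be taken for a device effect about half the time. That figure (51% in Step 3) needs three things that the protocol does not state: that ±5% is the confidence half-width of the mean change, that success means rejecting zero mean change, and that the drift equals that half-width. Given the first two, the third makes the answer about one half by construction. Under the expectation that the protocol does state, the figure at the same SD is about 3%.

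A reader might likewise infer that recruiting more participants always makes a false claim more likely. That holds for the unstated mean test with a fixed positive drift. It is not a general property of this protocol.

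**Conclusion.** The mismatch is real and needs no numerical assumption. The aim, the effectiveness statement and the sample-size sentence each claim a change due to the device, while the procedures allow only the total within-person change to be estimated. The ±5% is at most a statement about sampling error of that total.

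The size of the resulting error cannot be derived from the documents. With an assumed 5% drift and no device effect, the protocol's own expectation would be met in about 3% to 27% of trials for SDs of 12.9 to 50, and with a 10% drift in about 42.5% whatever the SD. These figures rest on the assumed drift, normal changes and 28 completers. They illustrate dependence on unknown quantities and are not an error rate for this trial.

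The point should be corrected, because the wording governs what the trial may conclude.

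**What to change.** Change the protocol wording in these places:

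- **Specific aims** (Background, Rationale and Goals, Q3; Study Procedures, Q2) and the **effectiveness statement** (Background, Rationale and Goals, Q1): *to estimate the within-person change in hfHRV from baseline to week 4 during use of the unit*.
- **Sample-size justification** (Study Population, Q3): state that the ±5% refers to this total change, not to the part due to the device.
- **One added sentence**: without a concurrent control the change will not be attributed to the device, and it serves as preliminary data for a controlled study. This agrees with the preliminary-data remark already in the Background section.

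No procedure, visit or sample size changes. The cost is a narrower claim. A sham or untreated arm would allow attribution, but it is a larger redesign and is not requested here.
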